therefore the variation in time-point of when the ACEs survey is administered is not expected to affect the veracity of the reported responses.

Finally, all children will be assessed for developmental status around 12 months following enrollment at a time before the child turns 42 months 15 days. Parent's and children will have the option of attending the Seashore house on CHOP's main campus or the Robert's Center for Pediatric Research on CHOP's main campus, whichever is most convenient for the participant, to complete a measure of child developmental status (BSID-III) (Appendix 5). If the participant chooses the Seashore House, the Center for Human Phenomic Science will conduct the developmental assessment. If the participant chooses the Robert's Center for Pediatric Research, a clinician will conduct the developmental assessment. In the event in-person procedures cannot take place at the time of the final study visit time-point (due to COVID-19 or other reasons) this assessment may be performed beyond the 12-month time-point, at a later date, anytime before the child turns 42 months and 15 days old. EI data on referral completion, EI referral completion, EI eligibility, and EI services use will be obtained from Philadelphia Infant Toddler Intervention, a community partner on this proposal, to corroborate parent self-report. The Early Intervention data is collected and managed by the Philadelphia Infant and Toddler Early Intervention Program in the Department of Behavioral Health and Intellectual Disabilities Services.

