## **3.2 Allocation to Treatment Groups and Blinding**

In this study, 360 eligible children will be randomized 1:1 to the FN or usual care consisting of routine Child Find procedures. We chose a randomized design, because it is most effective at guarding against bias and will ensure that patients in both arms are similar in observed and unobserved characteristics. The initial randomization will be stratified by practice site, child sex, and age group (0-<18 months old and 18-30 months old) to ensure

balance between groups. We will control post-hoc statistically for any imbalances that arise. Allocation concealment (blinding of the treatment assignment) will be implemented using sealed, opaque envelopes, along with stratification, and randomly permuted blocks of unequal sizes (to prevent providers and patients from manipulating the randomization). Treatment assignment will be done at the time of enrollment following informed consent and patients will be followed over time with measures related to EI referral completion, EI services completion, and patient engagement collected at baseline, 3, 6, 9, and 12 months as well as child developmental status around 12 months.

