# 6 STATISTICAL CONSIDERATIONS

## 6.1 Primary Endpoint

In order to determine the effectiveness of the Opening Doors to Early Intervention Program on child developmental status, our primary outcome for this aim is the Bayley-III cognitive subscale measured at 12 months follow-up.

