## 6.3 Control of Bias and Confounding

Randomization and allocation concealment are the primary means of avoiding bias. Analytic strategies will also be used to control for residual confounding: (1) Stratification will control for imbalance not controlled by design. (2) Additional potential confounders will be evaluated for any residual association with treatment and included in model as needed. (3) Post randomization effects: The primary source of bias will arise after randomization from dropout and loss to follow-up. To address this problem and avoid missing data, we shall implement the following measures: (a) incentives to each family to complete the study, (b) collection of multiple contact numbers and tracking of changes, and (c) contact all randomized participants, even if they do not continue with their clinical contacts. Baseline data collection will include questions about factors that predict potential dropout, such as current living situations and regularity of contact with health care providers. (4) Our analytic model for treatment effect will include not only potential confounders but also predictors of dropout, to be able to relax assumptions about the missing data process. (5) To investigate the possibly informative dropout (for reasons related to the intervention), we will implement sensitivity analyses (6) For missing values in any of the outcome measurement tools, we will implement formal methods of multiple imputation. (7) We shall account for all dropouts and check all baseline information in real time for both invalid values and missing items and then prompt the child's caregiver for any corrections or clarifications. Then, if any covariates remain missing, we shall implement multiple imputation. (8) Attenuation bias from non-compliance might also occur if the child remains

in the study but fails to adhere to all aspects of the intervention. To address this potential problem, and to estimate the effect of treatment in the presence of full compliance, we will implement the methods outlined by Small and colleagues and by Nagelkerke. However, the “as randomized” approach will remain the primary method for assessing statistical significance of the intervention.

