### 6.4.2 Analysis of Primary Outcomes of Interest

#### 6.4.2.1 *Specific Aim 1*

##### Primary outcomes

In order to determine the effectiveness of the Opening Doors to Early Intervention Program on child developmental status, our primary outcome for this aim is the Bayley-III cognitive subscale measured at 12 months follow-up. For our primary outcome, a linear mixed effects approach will be used to model differences in cognitive functioning between intervention groups accounting for clustering due to practice. Such an approach is advantageous for offering flexible means for accounting for potential issues that arise in randomized trials. For example, baseline patient characteristics that were not balanced across intervention groups by the randomization process can be accounted for through covariate level adjustment. Also, differential drop-out and loss to follow-up between groups can be accounted for by incorporating missing data methods such as multiple imputation.

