### **6.5 Sample Size, Statistical Power and Analysis Plan**

Our target sample size accounting for clustering by practice site for patients with complete 12-month follow-up is 300 participants. Assuming at least an 80% follow-up rate, the number needed to recruit to obtain this final sample size is about 360. Since a partial goal of the proposed intervention is to increase patient engagement, the rate of drop out is likely to be lower among the intervention group. If we conservatively assume that the drop-out rate among control patients is double that of patients on the intervention, the sample of patients

with complete follow-up will consist of approximately 130 control patients and 170 intervention patients.

Using the Bayley-III cognitive subscale as a primary outcome, we assert that the proposed intervention would be successful if it resulted in an increase of 3 points or more on this subscale. This is the minimal clinically significant outcome difference. Thus, based on the proposed sample size, we would obtain 96% power to detect a clinically meaningful difference in the Bayley-III cognitive scores. The power was estimated based on a simulation study that assumed that the sole impact of the intervention was on increasing enrollment into EI. Based on expected cognitive improvements due to EI found by Guralnick et al, we further assume that children who enrolled in EI had an average increase over a 12 month period of 10 points on the cognitive scale with a standard deviation of 1 point compared to patients who did not enroll. Based on these assumptions, an increase of 3 points on the cognitive scale between the intervention and control group would be the result of an increased rate of enrollment from 50% among controls to 80% among the intervention group. These rates of enrollment are consistent with rates suggested by our pilot data (Preliminary Studies Section).

**Figure 1** *Assessment of power to detect a clinically meaningful difference*

Power	n	
0.96	300	Assuming a minimal clinically significant outcome difference ( $\geq 3$ points increase in the BSID-III cognitive subscale)

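### Protocol 6.3 and the SAP do not ensure an unbiased all-randomised Bayley estimate: the dropout predictors described are baseline ones, and the imputation variables that the plan's own mechanism calls for are not named

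*Protocol*

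**What the plan says.** Protocol 6.1 defines the endpoint: "our primary outcome for this aim is the Bayley-III cognitive subscale measured at 12 months follow-up". Section 3.2 fixes the population: "360 eligible children will be randomized 1:1 to the FN or usual care". Section 6.3 keeps the analysis by randomised arm as primary.

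On dropout, Protocol 6.3 item (3) says "Baseline data collection will include questions about factors that predict potential dropout" and gives current living situation and regularity of provider contact as examples. Item (4) says "Our analytic model for treatment effect will include not only potential confounders but also predictors of dropout". Item (5) plans sensitivity analyses for informative dropout, and item (6) plans multiple imputation of missing outcomes. Section 6.4.2.1 repeats, beside the primary model, that "differential drop-out and loss to follow-up between groups can be accounted for by incorporating missing data methods such as multiple imputation". None of these places lists the imputation variables or defines the sensitivity analyses.

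Protocol 6.5 gives the mechanism. On dropout: "Since a partial goal of the proposed intervention is to increase patient engagement, the rate of drop out is likely to be lower" in the intervention arm. On the effect, the power simulation assumed that "the sole impact of the intervention was on increasing enrollment into EI".

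On available data, Protocol 3.1.1 says "EI data on referral completion, EI referral completion, EI eligibility, and EI services use will be obtained from Philadelphia Infant Toddler Intervention", with the stated purpose of corroborating parent report. Protocol 5.1.2.1 collects engagement at baseline and every three months.

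The SAP analysis for Hypothesis 1c compares Bayley scores by arm, adjusting for sex, age and primary care site. It names no missing-data method.

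**The concern.** The variables the plan describes as dropout predictors are not the ones that its own mechanism makes important. If families who never enrol in EI are also the ones who miss the Bayley visit, scores are not missing at random given arm and baseline variables. Adjusting for living situation or provider contact, or imputing from arm and baseline variables, then leaves the bias in place. So does the SAP model with sex, age and site.

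Control completers would look more often enrolled than the control arm really is. Protocol 6.5 treats 3 points as the smallest difference that counts as success, so a modest shortfall could place a programme that meets this threshold below it.

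The remedy has to sit in the right model. EI enrolment and engagement are on the causal pathway. They help in an imputation model but do harm as covariates in the treatment-effect model.

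**Working it through.** **Inputs from the documents.** 360 children randomised 1:1, so 180 per arm (Protocol 3.2). About 300 evaluable, so 60 lost (3.3.2). At least 80% follow-up, control dropout double that of intervention, EI enrolment 50% v 80%, and a 10-point gain with EI (6.5).

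**Plan's own effect.** 10 × (0.80 − 0.50) = 3.0 points. This reproduces.

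**Losses by arm.** With 60 lost and a 2:1 ratio: 40 control (40/180 = 22.2%) and 20 intervention (20/180 = 11.1%), leaving 140 and 160 completers. At exactly 80% follow-up, 72 are lost: 48 and 24. The 130 and 170 completers printed in 6.5 imply 50 v 10 lost, which is 5:1 and not double, so they are not used here.

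**Assumption not in the documents.** Within each arm, non-enrolled families are k times as likely to be lost, with the same k in both arms. Baseline variables are taken to carry no information on enrolment; the simulation below relaxes this.

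**Formula.** With enrolment p and arm dropout d, loss among the enrolled is x = d / [p + (1 − p)k]. Enrolment among completers is p(1 − x) / (1 − d). The estimated effect is 10 × (intervention − control).

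**Worked case, k = 2, 40 v 20 lost.**
- Control: x = 0.2222/1.5 = 0.1481; completers enrolled = 0.5 × 0.8519/0.7778 = 54.8%.
- Intervention: x = 0.1111/1.2 = 0.0926; completers enrolled = 0.8 × 0.9074/0.8889 = 81.7%.
- Effect: 10 × (0.8167 − 0.5476) = 2.69.

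| Loss (control v intervention) | k = 1 | k = 1.5 | k = 2 | k = 3 |
|---|---|---|---|---|
| 40 v 20 | 3.00 | 2.81 | 2.69 | 2.57 |
| 48 v 24 (20% overall) | 3.00 | 2.75 | 2.60 | 2.44 |

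**Direction.** With 40 v 20 lost, but k = 1 in control and k = 3 in intervention, completers are 50.0% and 82.9% enrolled. The estimate is 3.29, away from zero.

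**If enrolment alone drove loss, at the same rates in both arms.** Solving 0.5a + 0.5b = 0.2222 and 0.2a + 0.8b = 0.1111 gives 40.7% loss among non-enrolled and 3.7% among enrolled children (k = 11). Completers are then 61.9% and 86.7% enrolled, giving 2.48.

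**Simulation of that last case.** There were 2,000 runs per setting, with assumed background SD of 1, 7 or 15 and assumed latent correlation of 0 to 0.9 between a baseline predictor and enrolment.

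| Method | Estimated effect |
|---|---|
| Full data | 2.95 to 3.06 |
| Baseline predictor in the treatment-effect model | 2.48 to 2.69 |
| Imputation from arm + baseline | 2.48 to 2.68 |
| Imputation from arm + baseline + EI enrolment | 2.95 to 3.07 |
| EI enrolment as covariate in the treatment-effect model | about 0 |

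Even a baseline predictor correlated 0.9 with enrolment recovers only part of the shortfall. EI enrolment in the imputation model recovers all of it within simulation error.

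**The case against.** The strongest reply is that 6.3 does more than item (4). A reader might infer that bias remains even when 6.3 is followed in full. The documents do not support that. Items (5) and (6) and section 6.4.2.1 allow imputation with EI status, and nothing restricts imputation to baseline variables. An analyst who chose the county records would remove the bias from this mechanism. The word baseline is also inferred for item (4) from the sentence before it. This part of the reply stands: the plan leaves the result to an unstated choice; it does not fix a wrong one.

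A reader might also infer that the bias must run towards zero. It need not. The documents give no k, they do not say that non-enrolled families within an arm are lost more often, and the 3.29 case runs the other way. The sole-pathway statement is an input to a power simulation, not a finding.

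A third tempting reading is that item (4) puts engagement or EI enrolment into the primary model and wipes out the effect. That is unlikely. Section 6.3 keeps the by-arm analysis primary, and 6.4.2.2 adds engagement only in separate Aim 2 models.

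Nor are EI data collected for corroboration alone: EI referral and service completion are secondary outcomes in 6.2, and the SAP uses EI measures as outcomes and mediators. What holds is that no section assigns them to the imputation.

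Finally, the bias is modest against sampling error. With 40 v 20 lost it is 0.19 to 0.43 points. The standard error with 140 and 160 completers is SD × √(1/140 + 1/160) = SD × 0.116, or about 0.6 at an assumed SD of 5 and 1.7 at 15.

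**Conclusion.** The point holds as a gap in the method that can be closed cheaply. Baseline adjustment, baseline-only imputation and the SAP's sex, age and site model all leave bias whenever non-enrolled families are lost more often. Copying 6.3 into the SAP unchanged would not settle it, because 6.3 does not say what enters the imputation.

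At 40 v 20 lost and k from 1.5 to 3, the shortfall is 6% to 14% of the 3-point effect (0.19/3.0 and 0.43/3.0). At 20% overall loss it is 8% to 19% (0.25/3.0 and 0.56/3.0). These sizes rest on the enrolment rates and 10-point gain in 6.5, on an assumed k, and on the same k in both arms. The bias is nil at k = 1 and can reverse under arm-specific loss. It would be wrong to read this as showing that 6.3 necessarily understates the effect.

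**What to change.** Reword Protocol 6.3 items (4) to (6) and the SAP analysis for Hypothesis 1c as follows.

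- **Treatment-effect model:** arm and baseline variables only, with no variable measured after randomisation.
- **Imputation model:** multiply impute missing Bayley scores by arm, or with arm interactions. Use the same baseline variables plus, as auxiliary variables in this model only, EI referral completion, EI enrolment or first service, and service use from the county records, together with the observed EI Engagement scores.
- **Primary estimate:** the pooled arm coefficient. Define the item (5) informative-dropout analyses and apply them on top, since loss that depends on the unseen Bayley score itself is not cured by auxiliary variables.

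The cost is wording and a slightly larger imputation model. No new data are needed: the county records (Protocol 3.1.1), the release form (9.5.1) and the quarterly engagement scores (5.1.2.1) are already planned. The downside is that EI status must itself be imputed for families who withdraw the release or move out of Philadelphia County, and some of these may be the families lost to follow-up.

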ODEI Study Statistical Analyses Plan

Title: The Opening Doors to Early Intervention Study (ODEI)

NCT Number: NCT03625115

Document Date: July 3rd, 2024

ODEI Study Statistical Analyses Plan

Aim 1: To test the effectiveness of the Opening Doors to Early Intervention Program on EI service use and child developmental status among poor minority children residing in an urban community.

- a. *Hypothesis 1a:* A greater proportion of children who are randomized to the intervention will complete EI referrals than children in the control condition at 12 months.

Analysis: Chi square analysis on the difference in completion of MDE by study arm and logistic regression on the difference in MDE completion by arm, controlling for sex, age, and primary care site.

- b. *Hypothesis 1b:* Among children eligible for EI services, children randomized to the intervention will initiate EI services at a greater rate & receiving a longer duration of EI services than children in the control condition.

Analysis: Chi square test on the difference in EI service initiation by arm and logistic regression, controlled for sex, age, and primary care site. Survival analysis with a Kaplan-Meier curve of EI duration of services by arm.

- c. *Hypothesis 1c:* As a result, children who are randomized to the intervention will have more favorable developmental outcomes than children in the control condition at 12 months.

Analysis: Logistic regressions to determine the difference in cognitive and language BSID III scores by arm, controlling for sex, age, and primary care site.

Variable Definitions:

- Completion of EI Referrals: Completion of Multidisciplinary Evaluation (MDE)
- Initiating EI services: Date of first early intervention service
- Duration of EI services: The time between the EI service initiation and discharge from early intervention OR 12 months from randomization (if discharge date is unavailable)
- Developmental outcomes: Language and cognitive composite scores from BSID III assessment.

Aim 2: To assess whether parent engagement mediates the effects of the Opening Doors to Early Intervention Program.

- a. *Hypothesis 2a:* Parent engagement will mediate the association between program participation and completion of EI referrals and participation in EI services (duration).

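### The SAP's Bayley models do not carry forward the protocol's handling of dropout: their covariates omit the required dropout predictors, and nothing is said on imputation or informative-dropout sensitivity analysis

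*Protocol*

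**What the plan says.** Protocol section 6.3 names dropout after randomization as the primary source of bias and makes these commitments:

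- Item 4: the treatment-effect model "will include not only potential confounders but also predictors of dropout".
- Item 5: "To investigate the possibly informative dropout (for reasons related to the intervention), we will implement sensitivity analyses".
- Item 6: where any outcome measure is missing, "we will implement formal methods of multiple imputation".
- Item 7: "if any covariates remain missing, we shall implement multiple imputation".

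Section 6.4.2.1 mentions multiple imputation again for the primary outcome, but only as something that can be used.

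Section 6.5 expects loss to depend on arm: "the rate of drop out is likely to be lower among the intervention group". It then assumes twice the dropout rate in controls and gives about 130 control and 170 intervention completers out of 300.

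The SAP, dated July 2024, writes out the Bayley analysis under Hypothesis 1c as regressions for "cognitive and language BSID III scores by arm, controlling for sex, age, and primary care site". The Aim 3 models add one moderator at a time. The SAP defines no analysis set and gives no rule for a missing Bayley score. Its only missing-value rule concerns an unavailable EI discharge date.

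**The concern.** The two documents differ in two distinct ways. The SAP's covariate list is explicit, and it is not the list that item 4 requires. On imputation and on sensitivity analysis the SAP simply says nothing.

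The gap matters because of how the primary outcome is collected. Table 1 schedules the Bayley once, at the 12-month visit, and section 3.1.1 requires attendance at one of two campus locations. With no earlier Bayley score in the model, neither the SAP's regression nor the protocol's linear mixed model can recover anything for a child who is never assessed. By default, such children drop out of the fit.

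If loss differs by arm and the lost families differ in child development, the remaining comparison is not the as-randomized one that section 6.3 calls primary. The protocol also never fixes the imputation model, the form of the sensitivity analysis, or which result is primary. If the SAP does not fix them either, they can be chosen after the data are seen.

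**Working it through.** **Inputs.** 360 children randomized 1:1, so 180 per arm (protocol 3.2). 300 completers, control dropout rate twice the intervention rate, stated completers 130 and 170, 3-point minimal difference, EI enrolment 50% versus 80%, and a 10-point gain from EI (all protocol 6.5).

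**Step 1: reproduce the completer split.**
- 360 − 300 = 60 lost. At 2:1 that is 40 control and 20 intervention, leaving 140 and 160. Loss is 40/180 = 22.2% and 20/180 = 11.1%.
- The stated 130 and 170 mean 50 and 10 lost: 27.8% and 5.6%, a ratio of 5:1.
- Taking 80% follow-up literally does not help. 72 lost from 360 gives 132 and 156. Randomizing 300/0.80 = 375 with 75 lost gives 137.5 and 162.5. No variant yields 170.

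The stated split is therefore not reproduced from the stated premise. Both splits are carried forward, with the 2:1 premise first.

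**Step 2: shift in a complete-case difference.** Suppose unassessed children score d points below assessed children in both arms. With loss fractions L_C (control) and L_I (intervention), each arm's full mean is its completer mean minus L × d. Hence

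complete-case difference = full difference − (L_C − L_I) × d.

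For d > 0 and heavier control loss, the estimate moves towards the null. The documents give no value for d; 5 and 8 are assumptions.

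| Completers | L_C − L_I | d = 5 | d = 8 |
|---|---|---|---|
| 140 / 160 | 20/180 = 0.111 | 0.56 | 0.89 |
| 130 / 170 | 40/180 = 0.222 | 1.11 | 1.78 |

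**Step 3: the same check on the protocol's own enrolment model.** The true difference is 10 × (0.80 − 0.50) = 3.0. Of 180 per arm, 90 controls and 144 intervention children enrol.
- Dropout unrelated to enrolment: 3.0, no bias.
- All lost children never enrolled: 10 × (144/160 − 90/140) = 2.57; at 130/170, 10 × (144/170 − 90/130) = 1.55.
- All lost children enrolled: 10 × (124/160 − 50/140) = 4.18; at 130/170, 10 × (134/170 − 40/130) = 4.81.

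The last two are extremes. In all of these cases loss depends only on EI enrolment, so imputation conditional on enrolment recovers 3.0 in expectation. The shift d in Step 2 is different when it comes from unmeasured causes: imputation under missing-at-random leaves it in place.

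**The case against.** The strongest reply is that the SAP withdraws nothing. It is a short outline by hypothesis, it does not claim to replace section 6.3, and the protocol's commitments to imputation and sensitivity analysis can be read as still in force. That stands for those two items. A reader might infer that the sponsor has abandoned imputation or has chosen a complete-case analysis; the documents support neither. Complete-case is what the listed regressions do by default, not something the SAP states. The reply does not cover the covariate list, which is explicit and omits what item 4 requires.

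Further points in the plan's favour:

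- A reader might take 28% versus 6% loss as the plan's expectation. It follows from the 130/170 counts, but those contradict the doubling assumption, which section 6.5 itself calls conservative. The 2:1 figures are the ones to lead with.
- A reader might infer a risk of a false positive. With lost children scoring lower in both arms, the bias is towards the null. Only other patterns, such as losing mainly EI-enrolled children, inflate the difference.
- The SAP names logistic regression for Bayley composite scores without a cut-point, so its model cannot literally be run as written, and a bias in mean points presupposes a linear model such as the protocol's. That is a separate discrepancy.
- The protocol does not prescribe the form of the sensitivity analysis, so a tipping-point method is one reasonable option and not an obligation.

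**Conclusion.** The point holds as a failure to carry section 6.3 into the SAP: a direct conflict over covariates, and silence on imputation and informative-dropout sensitivity analysis. At the protocol's 2:1 dropout premise, a default complete-case difference would be understated by 0.11d, or 0.6 to 0.9 points for d between 5 and 8, against a 3-point minimal difference. At the stated 130/170 the range is 1.1 to 1.8 points.

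This rests on a linear comparison of means, the same d in both arms, and values of d that are assumed. If dropout is unrelated to outcome within arm there is no bias, but section 6.3 declines to rely on that. The change should be made; it does not call the design into question.

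**What to change.** In the SAP:

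1. Make multiple imputation the primary Bayley analysis. The imputation model should hold study arm, the analysis covariates, the baseline dropout predictors actually collected, StimQ, income, maternal education, follow-up engagement, and enrolment and service data from the EI agency. Engagement and EI use arise after randomization, so they belong in the imputation model and not in the treatment-effect model.
2. Bring the covariate list into line with item 4 of section 6.3 by adding the dropout predictors, or amend the protocol and give the reason.
3. Define the primary analysis set and report complete-case as supporting.
4. Pre-specify an arm-specific sensitivity analysis for informative dropout, for example delta-adjusted imputation carried to a tipping point. Imputation under missing-at-random does not remove loss driven by unmeasured factors.
5. Reconcile 130/170 with the doubling assumption, and 360 recruited with 80% follow-up.

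The cost is SAP text and modest programming. One item needs checking: section 6.3 promises baseline questions on living situation and regularity of health-care contact, but the baseline measures listed in Table 1 and sections 3.1.1, 4.1.1 and 5.1.2.1 do not name the latter, and the demographic form is not in the documents reviewed. If the imputation model is limited to what was collected, no new data are needed.
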